### 3.2.2.b Emergent Treatment

In emergency situations when a patient meets all other eligibility criteria and has had baseline required observations as outlined in [Section 7.4](#) or [7.5](#), but is too ill to undergo a biopsy safely, the patient may be enrolled on AHEP0731 without a biopsy.

Clinical situations in which such emergent treatment may be indicated include, but are not limited to, the following circumstances:

- a. Anatomic or mechanical compromise of critical organ function by tumor (eg, respiratory distress/failure, abdominal compartment syndrome, urinary obstruction, etc)
- b. Uncorrectable coagulopathy

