**For a patient to maintain eligibility for AHEP0731 when emergent treatment is given, the following must occur:**

- The patient must have a clinical diagnosis of hepatoblastoma, including an elevated alphafetoprotein, and must meet all AHEP0731 eligibility criteria at the time of emergent treatment.
- Patient must be enrolled on AHEP0731 prior to initiating protocol therapy. Per protocol [Section 3.2.9](#), a patient will be ineligible if any chemotherapy is administered prior to AHEP0731 enrollment.
- If the patient receives AHEP0731 chemotherapy PRIOR to undergoing a diagnostic biopsy, pathologic review of material obtained in the future during either biopsy or surgical resection must either confirm the diagnosis of hepatoblastoma or not reveal another pathological diagnosis to be included in the analysis of the study aims.

**PATIENTS WILL BE STAGED FOR RISK CLASSIFICATION AND TREATMENT AT DIAGNOSIS USING COG STAGING GUIDELINES**, as listed in [Appendix III](#).

At the time of study enrollment, the patient's treatment regimen must be identified. If the patient's primary tumor was resected prior to the day of enrollment and a blood specimen for the determination of serum alphafetoprotein was not obtained prior to that surgery, the patient will be considered to have alphafetoprotein of greater than 100 ng/mL for the purpose of treatment assignment. If tumor samples obtained prior to the date of enrollment were not sufficient to determine whether small cell undifferentiated (SCU) histology was present, treatment assignment will be made assuming SCU is not present in the tumor.

For patients with Stage I or II disease, specimens for rapid central review have been submitted and the rapid central review diagnosis and staging must be available to be provided on the AHEP0731 Eligibility CRF.

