## **8.0 CRITERIA FOR REMOVAL FROM PROTOCOL THERAPY AND OFF STUDY CRITERIA**

### **8.1 Criteria for Removal from Protocol Therapy**

- a) Progressive disease.
- b) Unresectability of tumors following 4 cycles of chemotherapy in intermediate-risk patients.
- c) Unresectability of tumors following 10 cycles of chemotherapy in high-risk patients who responded (RECIST CR or PR) to “up-front” window therapy.
- d) Unresectability of tumors following 8 cycles of chemotherapy in high-risk patients who did not respond to “up-front” window therapy.
- e) Inability to have a liver transplant by the specified protocol timepoints for reasons unrelated to hepatoblastoma.
- f) Failure to begin protocol therapy within 42 days of initial biopsy or definitive surgery whichever occurs last.
- g) Failure to resume post resection chemotherapy within 42 days of resection in intermediate- or high-risk patients.
- h) Refusal of further protocol therapy by patient/parent/guardian.
- i) Completion of planned therapy.
- j) Physician determines it is in patient’s best interest.
- k) Development of a second malignant neoplasm.
- l) For high-risk patients, if the investigator selects a post-induction regimen that is not indicated by the central review of response.

Patients who are off protocol therapy are to be followed until they meet the criteria for Off Study (see below). Follow-up data will be required unless consent was withdrawn.

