### **8.2 Off Study Criteria**

- a) Death.
- b) Lost to follow-up.
- c) Patient enrollment onto another COG study with tumor therapeutic intent (eg, at recurrence).
- d) Withdrawal of consent for any further data submission.
- e) Tenth anniversary of the date the patient was enrolled on this study.
- f) Definitive surgery does not confirm the diagnosis of hepatoblastoma or reveals another pathological diagnosis in patient who was enrolled emergently without initial biopsy because too sick.

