### 9.2 Statistical Analysis Methods

#### Statistical Considerations

Patients will be enrolled to the study for Five years and followed for an additional year, by which time we expect most disease-related analytic events will have occurred. The design objectives will be different for the four subgroups: (1) Stage I PFH patients (stratum 1) with AFP  $\geq$  100 ng/mL or AFP not obtained prior to surgical resection of tumor; (2) low risk patients (stratum 2) defined as patients with Stage I non-PFH, non-SCU; Stage II non-SCU (3) intermediate risk patients (stratum 3); and (4) Stage IV patients or patients with AFP < 100 ng/mL at diagnosis (stratum 4). EFS will be the time from patient enrollment until last follow-up or an analytic event is observed, whichever comes first. Analytic events are: (1) progression of existing disease or occurrence of disease at new sites; (2) treatment failure defined as the presence of disease after four cycles of chemotherapy and post-induction surgery (if attempted) for patients enrolled with Stage III disease or presence of disease after planned chemotherapy (eight cycles for non-responders, ten cycles for responders) for patients enrolled with Stage IV disease (3) death from any cause prior to disease progression or diagnosis of a second malignant neoplasm; or (4) diagnosis of a second malignant neoplasm. Survival will be the time from enrollment until death from any cause or last follow-up, whichever comes first.

[Section 3](#) requires that planned start of systemic therapy for patients whose protocol prescribed therapy includes chemotherapy must be within 42 days of enrollment. Experience from prior COG studies of hepatoblastoma demonstrates that this can be accomplished in most patients. All patients who die within 42 days of enrollment will be considered in the analytic plans below. All patients who survive more than 42 days after enrollment and whose protocol therapy prescribes chemotherapy but who do not have such systemic therapy started by the 43rd day after enrollment will be excluded from the analyses below.

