A patient enrolled without histological confirmation (see [Section 3.2.2.b](#)) will be considered evaluable for all study analyses unless the tumor tissue obtained in a future surgical procedure is not consistent with hepatoblastoma or reveals another pathological diagnosis. If histological confirmation is not confirmed in the future for these patients by a biopsy or surgical resection, they will be considered off study.

The statistical analysis will include an assessment of the influence of the exclusion of cases for whom there is a discrepancy in diagnosis between institutional and central review, or for whom there is an atypical histological presentation. The influence will be assessed by comparing the EFS and survival, as estimated by the method of Kaplan and Meier with and without such cases. This will provide an *ad hoc* assessment of the effect of such cases on outcome characterization. Formal statistical quantification of such effects will not be straightforward.

Surgical resection followed by observation was first tested on COG trial P9645 and has been demonstrated to be a successful approach for patients with stage I PFH. These patients will be enrolled on the trial, since

it will be necessary to submit all Stage I and II patients to mandatory central review to determine the appropriate analytic strategy. The results of this review will be returned for information to the relevant institutional investigator. Individuals considered Stage I PFH and treated with surgery only will be considered for the analysis described in the paragraph below. Individuals considered Stage I non-PFH, non-SCU, Stage II, non-SCU patients and treated with the chemotherapy for such patients will be considered in the analysis described in "[Hypothesis 1.1](#)" below.

[figure not shown]

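### Patients enrolled emergently without biopsy: the rules on analysis and follow-up conflict when later tissue is non-diagnostic, and Section 9.2 says two things when there is no later tissue

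*Combined protocol and SAP*

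**What the plan says.** Section 3.2.2.b covers the emergency case: if someone "is too ill to undergo a biopsy safely, the patient may be enrolled on AHEP0731 without a biopsy". It refers to the baseline work-up in Sections 7.4 and 7.5, so the route leads to Strata 3 and 4. It requires a clinical diagnosis with elevated AFP. Of material obtained after chemotherapy has begun, it says that the review "must either confirm the diagnosis of hepatoblastoma or not reveal another pathological diagnosis to be included in the analysis of the study aims".

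Section 8.2(f) lists as an off-study reason: "Definitive surgery does not confirm the diagnosis of hepatoblastoma or reveals another pathological diagnosis in patient who was enrolled emergently without initial biopsy".

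Section 9.2 has two consecutive sentences. By the first, such a patient "will be considered evaluable for all study analyses unless the tumor tissue obtained in a future surgical procedure is not consistent with hepatoblastoma" or shows another diagnosis. The second reads: "If histological confirmation is not confirmed in the future for these patients by a biopsy or surgical resection, they will be considered off study".

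Off-study status matters because of the closing text of Section 8.1: "Patients who are off protocol therapy are to be followed until they meet the criteria for Off Study". Section 9.2 does protect early deaths: "All patients who die within 42 days of enrollment will be considered in the analytic plans below".

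**The concern.** Two kinds of patient fall between these rules. In one, tissue is obtained but is non-diagnostic, for example a post-chemotherapy resection with no viable tumor and no sign of another disease. In the other, no tissue is ever obtained.

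Neither state is fixed at entry. Tissue is obtained only if the child lives long enough and becomes well enough or operable. Whether it still contains recognizable tumor depends on the response to chemotherapy. A rule that ends follow-up on either ground selects on something related to outcome. Non-diagnostic tissue will tend to come from good responders, and absent tissue from children who did badly. If follow-up of these children stops, later relapses and deaths go unrecorded and the censoring is informative for EFS and survival. The two selections push in opposite directions, so the net bias cannot be assumed to have a particular sign.

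Two analysts could also handle the same patient differently, each citing the protocol.

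**Working it through.** **Step 1. Set the rules side by side.**

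| Later pathology | 3.2.2.b | 8.2(f) | 9.2, first sentence | 9.2, second sentence |
|---|---|---|---|---|
| Confirms hepatoblastoma | in analysis | stays on study | evaluable | stays on study |
| Shows another diagnosis | out of analysis | off study | not evaluable | off study |
| Tissue obtained, neither of these | in analysis | off study, if from definitive surgery | unclear | off study |
| No tissue obtained | no rule | not triggered | evaluable | off study |

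The first two rows agree. In the third, 3.2.2.b needs only the absence of another diagnosis, while 8.2(f) and the second sentence of 9.2 need positive confirmation. The first sentence of 9.2 turns on consistency with hepatoblastoma, which does not settle a specimen without viable tumor. In the fourth row only 9.2 speaks, and its two sentences point different ways. It also gives no date by which confirmation must have come, so the day on which follow-up ends is undefined.

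**Step 2. See what is already protected.** Section 9.2 counts progression, death and disease remaining after planned therapy as EFS events, and Section 4.6 says the same of high-risk tumors still unresectable at the end. An event recorded before the patient goes off study is not erased by any passage. Deaths within 42 days of enrollment stay in. The Stratum 3 toxic-death rule counts everyone given one dose of C5VD. What remains exposed is follow-up after the off-study date: relapse and death after a non-diagnostic resection, and survival in patients who never have tissue.

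**Step 3. Illustrate the size.** The plan gives no figure to reproduce and no count of emergent enrollments. Assume a crude EFS proportion in 41 patients, the Stratum 4 evaluable target, with S event-free.

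Removing one failure changes EFS from S/41 to S/40:

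S/40 − S/41 = S/(41 × 40) = EFS/40.

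Removing one event-free patient gives (S − 1)/40 − S/41 = −(1 − EFS)/40.

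EFS values for Stage IV or high-risk disease are taken from the protocol: 25% (INT-0098, Section 2.3.3), 56% (SIOPEL-3HR, Table 2) and 77% (SIOPEL-4, Table 2).

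| EFS | One failure removed | One event-free patient removed |
|---|---|---|
| 25% | 25/40 = +0.6 points | 75/40 = −1.9 points |
| 56% | 56/40 = +1.4 points | 44/40 = −1.1 points |
| 77% | 77/40 = +1.9 points | 23/40 = −0.6 points |

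These figures are for outright removal. For a patient who is censored and fails later, the effect depends on when censoring falls, and the documents do not allow that to be dated.

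**The case against.** The strongest reply is that off study is not the same as out of the analysis. The Section 8.2 list also includes death, loss to follow-up and the tenth anniversary of enrollment, and none of these removes data already collected. On that reading the two sentences of Section 9.2 can coexist: the patient is evaluable, and follow-up ends. This stands in part. It reduces the issue from exclusion to censoring, but the censoring is still tied to outcome, and the clash between 3.2.2.b and 8.2(f) over non-diagnostic tissue remains unresolved.

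Some stronger readings are tempting but not supported:

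- A reader might infer that the worst outcomes disappear from EFS. Events already observed count, and so do deaths within 42 days. Staying unresectable does not mean having no tissue either, since a later biopsy is accepted.
- A reader might put the effect at 1/41 = 2.4 points for each failure dropped. That keeps the denominator at 41 and treats the failure as event-free. Dropping a patient takes one from the denominator as well, which gives EFS/40.
- A reader might infer that the Stratum 4 decision, which turns on 22 versus 23 responders of 41, is at risk. Response is set at the end of Cycle 2 from imaging and AFP, and the evaluability definition does not mention off-study status. Evaluability does require eligibility, which 3.2.2.b links to later pathology, so the most that can be said is that the count is not clearly affected.
- A reader might take all three sections to conflict over absent tissue. They do not: 3.2.2.b is silent and 8.2(f) needs definitive surgery.

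It might also be said that Section 9.2 already compares Kaplan-Meier curves with and without doubtful cases. That comparison names discrepancies between institutional and central diagnosis and atypical histology. It does not name patients who were never confirmed.

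**Conclusion.** The point holds as a conflict of rules. For non-diagnostic tissue, Section 3.2.2.b includes the patient, while Section 8.2(f) and the second sentence of the Section 9.2 paragraph end required follow-up. For absent tissue, Section 9.2 alone applies and makes the patient both evaluable and off study. Applied as written, Sections 8.2(f) and 9.2 can informatively censor EFS and survival in Strata 3 and 4.

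The size cannot be judged from the documents, because they give neither the number of emergent enrollments nor how often later tissue is absent or non-diagnostic. The 0.6 to 1.9 points per removed failure is an illustration. It rests on a denominator of 41, a crude proportion, EFS of 25% to 77%, and removal rather than censoring. The documents do not show that off-study status deletes data already collected.

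**What to change.** Use one rule in all three places, taken from Section 3.2.2.b: only tissue that shows a different diagnosis removes a patient.

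1. In Section 9.2, delete the sentence that puts unconfirmed patients off study.
2. In the sentence before it, drop the test of consistency with hepatoblastoma and keep only the finding of another diagnosis.
3. In Section 8.2(f), delete the limb on failure to confirm and keep the limb on another diagnosis.
4. State in Sections 3.2.2.b and 9.2 that patients with no later tissue, and patients with non-diagnostic tissue, stay evaluable and are followed for EFS and survival. This step is needed because the present wording of 3.2.2.b does not cover absent tissue.
5. Add a sensitivity analysis of EFS and survival without the never-confirmed patients.

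The cost is a few sentences, continued follow-up of what may be a handful of patients, and one extra run. The drawback is that an occasional case that is not hepatoblastoma may stay in. The clinical-diagnosis and elevated-AFP requirement in Section 3.2.2.b limits that, and the sensitivity analysis would show its influence.

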#### 1.2.2

To determine the feasibility and toxicity of adding doxorubicin to the chemotherapy regimen of C5V for children with intermediate-risk hepatoblastoma.

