##### 4.4.2 5-Fluorouracil: Slow IV Push over 2-4 minutes

600  $\text{mg}/\text{m}^2/\text{dose}$  (20  $\text{mg}/\text{kg}/\text{dose}$  for patients < 10 kg) on Day 2.

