##### 4.5.1 CISplatin: IV over 6 hours

100 mg/m^2/dose (3.3 mg/kg/dose for patients < 10 kg) on Day 1.

Recommended hydration and administration guidelines:

Urine specific gravity should be < 1.010 prior to starting cisplatin.

Hours -2 to 0: Prehydrate with 300 mL/m^2 D5 ½ NS + MgSO4 8 mEq/L + KCL 20 mEq/L.

Hours 0-6: Infuse CISplatin + mannitol 8000 mg/m^2 in 750 mL/m^2 NS @ 125 mL/m^2/hr.

Hours 6- 24: D5½NS+ MgSO4 8 mEq/L + KCL 20 mEq/L to run at 125 mL/m^2/hr.

4.5.2 5-Fluorouracil: Slow IV Push over 2-4 minutes

600 mg/m^2/dose (20 mg/kg/dose for patients < 10 kg) on Day 2.

4.5.3 VinCRISTine: IV Push over 1 minute or infusion via minibag as per institutional policy

1.5 mg/m^2/dose (0.05 mg/kg/dose for patients < 10 kg) [Maximum dose: 2 mg] on Days 2, 9 and 16.

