Nine (9) stage I PFH patients will be required for AHEP0731. We may enroll up to 12 patients to account for patients who are determined later to be ineligible. These patients will be followed closely for disease and life status. The outcome of these patients will be summarized through survival and EFS curves estimated by the method of Kaplan and Meier. If 2 or more analytic events are observed, the strategy of surgery without any further therapy will identify enrollment to this strategy for possible termination because of insufficient disease control. If this strategy is associated with a long-term event-free survival of 65%, the probability of accepting it is 0.12. If this strategy is associated with a long-term event-free survival of 93%, the probability of accepting it is 0.89.

Toxicity will be reported using CTCAE criteria (version 4). All Grade 3 or 4 or greater non-hematological toxicities as well as any toxicity that requires submission of an CTEP-AERS report as outlined in protocol [section 11.3](#), Table B, will be reported while the patient is on protocol therapy. The frequency of each toxicity type will be quantified as the percent of reporting periods on which the toxicity of the relevant grade is reported. All reporting periods where the patient receives at least one dose of each of the agents in the therapeutic plan for that individual will be included in the denominator for the rate calculation.

Follow-up data will be obtained on all patients considered eligible for the protocol. As part of the study design, slides sufficient to confirm the histological subtype of hepatoblastoma (PFH v. SCU v. neither PFH nor SCU) of all Stage I patients will be submitted to mandatory central review according to the time lines described above. Patients for whom the central review supports the therapeutic approach of the institutional investigator will constitute the analytic subgroup for each of the analyses planned for Stage I patients. The results of this review will be returned for information to the relevant institutional investigator as soon as the assessment becomes available in the COG data system.

Hypothesis 1.1: (Stage I, non-PFH, non- SCU, Stage II, non-SCU [Stratum 2]): Expected Annual Accrual: 9.2 patients per year. Total: 51 patients. We may enroll up to 60 patients to account for patients who are determined later to be ineligible.

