If 7 or more analytic events are observed the strategy of surgery with reduced chemotherapy will identify enrollment to this strategy for possible termination because of insufficient disease control. If this strategy is associated with a long-term event-free survival of 78%, it will be rejected with probability 0.90. If this strategy is associated with a long-term event-free survival of 89%, it will be accepted with probability 0.81. The graph below describes the probability of accepting the strategy as a function of its long-term EFS:

Hypothesis 1.2 (Intermediate-risk patients [Stratum 3]): As of Amendment #3B enrollment to stratum 3 is terminated because sufficient patients have been enrolled to address the hypothesis. The total enrollment to stratum 3 was 105 patients.

*Feasibility of Delivery of C5VD*: The primary measure of feasibility will be rate of death as a first analytic event. All patients who receive at least one dose of the C5VD regimen will be considered evaluable for this endpoint. Any patient who dies on protocol therapy or within 30 days of the termination of protocol therapy of a cause considered possibly, probably or likely related to systemic chemotherapy will be considered to have experienced an on-protocol-therapy death. If five or fewer of the 99 patients experience on-protocol-therapy death, the regimen will be considered feasible for further development. If the regimen is associated with a death-event rate of 3%, that observed for patients who were assigned to chemotherapy on P9645, the regimen will be considered feasible with probability 0.92. If the regimen is associated with a death-event rate of 10%, the regimen will be considered not feasible with probability 0.94. If the sixth on-protocol-therapy death is reported, study enrollment will be suspended. In addition to this, at each report to the DSMC the estimated on-protocol-therapy death rate and its 95% confidence interval will be reported to the phase III DSMC as the cumulative incidence of on-treatment death and the 95% confidence intervals at four and six months.

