Since the addition of doxorubicin to C5V may affect the delivery of all the agents in the combination, we will characterize the amount of each agent that can be delivered during the first four cycles of therapy and the actual amount of doxorubicin delivered on protocol therapy. During the first four cycles, the total dose of each agent administered will be collected, along with the patient's height and weight. The average amount of each drug, calculated as dose per meter squared will be calculated and a lower 95% confidence bound on the true average dose delivered will be calculated assuming a normal distribution of delivered dose. In addition the total doxorubicin dose, in milligrams per meter squared will be calculated for each patient as well as the average and the 95% confidence interval for this amount. This will be used in planning subsequent trials.

Hypothesis 1.3: (Stage IV [Stratum 4]): Expected Annual Accrual: 16 patients per year. Total: 43 patients (to account for patients who may be later determined to be ineligible.)

Prior to Amendment 3B, VI therapy was evaluated in stage IV patients. No patient assigned to VI experienced early progression. All patients evaluated for the VIT combination, therefore, will be evaluated only for response as defined in Section 10 of the protocol.

[figure not shown]
Disease status at the end of two cycles of therapy (or earlier in the case of early progressive disease) will be the endpoint for evaluable patients.

A patient will be considered evaluable if the individual is eligible, receives at least one dose of each agent in the combination being tested and is not removed from protocol therapy for reasons other than toxicity or disease progression. Any evaluable patient who has a CR or PR according the criteria prescribed [Section 10](#) of the protocol will be considered a 'responder'. All other evaluable patients will be considered non-responders. Patients will be enrolled in two stages according to the design specified below:

Number of Evaluable Patients Enrolled	Results	Decision
Stage I: 22 Evaluable Patients	9 or fewer responders	Terminate the trial with the conclusion the regimen does not demonstrate sufficient disease control
	10 or more responders	Continue to the next stage and enroll 19 more patients
Stage II: 19 Evaluable Patients (Total of 41)	Cumulatively 22 or fewer responders	Terminate the trial with the conclusion the regimen does not demonstrate sufficient disease control

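### Graded toxicity is summarised only per reporting period, on a denominator that depends on the treatment received; a per-patient rate should be added

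*Combined protocol and SAP*

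**What the plan says.** The only analysis rule for graded toxicity is one paragraph of Section 9.2. On the measure it says: "The frequency of each toxicity type will be quantified as the percent of reporting periods on which the toxicity of the relevant grade is reported". On the denominator, it counts "All reporting periods where the patient receives at least one dose of each of the agents in the therapeutic plan for that individual". Toxicity is reported while the patient is on protocol therapy.

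The paragraph does not say whether the plan means the whole course, the agents due in that period, or the plan after dose modification. It does not say that events must come from the same periods as the denominator. The length of a reporting period is not stated; Section 7.5, footnote 13, refers to a Data Submission Schedule outside these documents.

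Primary aim 1.2.2 is "To determine the feasibility and toxicity of adding doxorubicin to the chemotherapy regimen of C5V" in intermediate-risk patients. Two other parts of that aim have rules of their own in Section 9.2: on-therapy death (a per-patient rule on 99 patients) and delivered dose. Section 11.9 covers the collection of Grade 3 or higher non-hematological events of any attribution, but gives no rate.

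**The concern.** There are two issues, of unequal strength.

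The first is that the denominator is conditional on treatment received. Section 5 directs that doxorubicin (5.2.1 to 5.2.4), cisplatin (5.3.2), vincristine (5.4.2) or temsirolimus (5.6) be left out for toxicity while other agents continue. If the plan is the one originally prescribed, a period in which an agent was left out throughout is dropped. The quantity being measured then helps to decide which periods are measured.

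The second is that a per-period percentage does not show how many children were affected. Six affected periods in one child count the same as one period in each of six children. For a primary aim about the toxicity of a more intensive regimen, the number of children affected is what a reader will look for, and nothing planned supplies it. The background figures in Section 2.3.2 are also on another scale: they give Grade 3-4 toxicity of C5V on P9645 cumulatively over four cycles, and hearing loss as 2 of 21 evaluable patients. A per-period rate cannot be set beside either.

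**Working it through.** **1. Stated figures.** The plan gives no figure for graded toxicity, so there is none to reproduce. The neighbouring toxic-death rule (feasible if 5 or fewer of 99) does reproduce. P(X ≤ 5 | n = 99, p = 0.03) = 0.922 against a stated 0.92, and P(X ≥ 6 | n = 99, p = 0.10) = 0.939 against a stated 0.94. That rule is not affected by this point.

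**2. Which periods fail, by reading of the plan.**
- *Plan as modified under Section 5:* a period with a directed omission still counts.
- *Plan as prescribed for the cycle:* a period in which an agent was omitted throughout fails.
- *Whole-course plan:* no single Regimen H cycle contains both the VIT and the C5VD agents (Section 4.1). Dexrazoxane is due only in Cycles 5 and 6 of Regimen F (Section 4.5.5), so with one-cycle periods 4 of 6 cycles would fail. This cannot be intended, but the wording allows it. The response rule for stratum 4 is tighter: "receives at least one dose of each agent in the combination being tested".

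**3. Early stops.** In C5V and C5VD, 5-fluorouracil and vincristine start on Day 2 and the other agents on Day 1 (Sections 4.4 and 4.5). A period that ends before Day 2 fails; one that ends on Day 3 or later passes. In VIT all three agents start on Day 1 (Sections 4.6.2 to 4.6.4).

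**4. Size of the denominator effect (assumed inputs).** Let r be the event rate in counted periods, f the fraction of periods excluded, and m the ratio of the event rate in excluded periods to r. With events and denominator from all periods:

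all-period rate = (1 − f)r + f·m·r

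With r = 10%:

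| f | m = 0.5 | m = 3 |
|---|---|---|
| 0.02 | 9.9% | 10.4% |
| 0.10 | 9.5% | 12.0% |
| 0.20 | 9.0% | 14.0% |

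The reported rate is 10% throughout, so the error can run either way. For a rough anchor on f, Section 2.3.3 gives 3 heart-failure cases in 81 patients on INT-0098, at other doxorubicin doses. Scaled to 99 patients this is 99 × 3/81 = 3.67. With an assumed 1 to 4 lost cycles each, out of 99 × 6 = 594, f is 0.6% to 2.5% and the all-period rate 9.9% to 10.5%. This covers one cause of omission only. If events came from all periods but were divided by counted periods alone, then f = 0.10 and m = 1 gives 0.10/0.90 = 11.1%.

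**5. Per-period against per-patient.** Assume 99 patients with six one-cycle periods each, and 30 periods with a given toxicity.
- Per period: 30/594 = 5.1%.
- Fewest patients: 30/6 = 5, so 5/99 = 5.1% (exact 95% CI 1.7% to 11.4%).
- Most patients: 30, so 30/99 = 30.3% (exact 95% CI 21.5% to 40.4%).

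With two-cycle periods: 30/(99 × 3) = 10.1% per period, from 30/3 = 10 patients (10.1%) to 30 patients (30.3%).

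Converting one rate to the other needs an assumption about clustering. If periods were independent, a 5% per-period rate over six periods would be 1 − 0.95⁶ = 26% of patients, but the plan gives no ground for independence.

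**The case against.** The best defence is that the rule refers to the plan for that individual, which may well mean the plan after Section 5 has been applied. On that reading directed omissions stay in, and only a C5V or C5VD period stopped before Day 2 is lost. Omissions are also narrower than they first look. For mucositis, doxorubicin is dropped only after toxicity at full dose, at 75% and at 50%, so from Cycle 4 at the earliest. One missed temsirolimus dose of the two in a cycle still satisfies the rule. If reporting periods span two cycles, as Section 7.5 suggests for the first period in stratum 4, a single-cycle omission need not exclude anything. A period without doxorubicin is arguably not informative about adding doxorubicin. All of this stands, and it limits the first issue to an ambiguity with a probably small effect. None of it supplies a per-patient rate.

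A reader might go further and infer three things that the documents do not support:
- *That periods cut short by acute toxicity are widely lost.* Every C5V and C5VD agent has been started by Day 2, and nothing in the documents suggests that stops between Day 1 and Day 2 are common.
- *That Section 9.2 contradicts itself,* because for toxic death "All patients who receive at least one dose of the C5VD regimen will be considered evaluable for this endpoint". That rule and the graded-toxicity rule serve different endpoints and may use different populations. Since the numerator is not restricted, it also cannot be said that a child treated on Day 1 only disappears from the table.
- *That the rule understates toxicity.* The direction depends on m, which is unknown.

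**Conclusion.** The point holds as a modest improvement. On any reading of the denominator, graded non-fatal toxicity has no planned per-patient summary, although toxicity of C5VD is part of a primary aim. In the illustration one table entry of 5.1% is compatible with 5.1% to 30.3% of children affected. That range rests on 99 patients, six one-cycle periods each and 30 toxicity periods, all assumed apart from the 99 patients and six cycles.

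The dependence of the denominator on toxicity is conditional on how the plan is read. Its direction is unknown and its size cannot be computed from the documents. No decision rule uses the table, and the rules for toxic death, delivered dose and response are untouched.

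**What to change.** In Section 9.2:
1. Define the denominator as every reporting period in which any protocol agent was given, and count events from those same periods.
2. Add, for each Grade 3 or higher non-hematological toxicity, the percentage of patients affected (worst grade over protocol therapy, with a 95% confidence interval) among all who received at least one dose of any protocol agent.
3. If a rate for the regimen as fully delivered is also wanted, keep the present restriction as a labelled secondary rate, limited to the agents due in that period.

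The cost is wording and minor programming; Section 11.9 already collects the events needed. The trade-off is that the main rates will describe the regimen as started, including periods in which an agent was omitted, and not as fully delivered. The secondary rate in item 3 keeps the other view available.
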